2.2.11 Safety Monitoring

No safety monitoring committees are planned for the study.

2.2.12 Interim Analysis

There are no formal interim analyses planned for this study, however, there will be an interim database freeze/lock of the study data after all subjects have completed their Off-Treatment Safety Follow-up Visit (Week 16). After this interim freeze/lock occurs, unblinding will occur and CTDS will produce the unblinded TLFs, except for the safety ophthalmic follow-up results. Once the final data has been collected and cleaned, the database will be locked and the ophthalmic safety results will be produced using the final, locked data. Blinded data review will occur periodically throughout the study (i.e. 50% of subjects who completed week 16, 75% of subjects who completed week 16) and any results that are produced will be clearly marked as “Blinded”.

2.2.13 Efficacy Analyses

The primary efficacy analysis population will be the ITT Population.

2.2.13.1 Primary Endpoint

The primary endpoint is the change from Baseline (Visit 2) to Week 12 (Visit 4) in the maximum daily pelvic pain (mean) using a standardized 11-point numerical rating scale (NRS) pain score recorded daily by an eDiary.

Average maximum pain scores will be summarized by week for each of the planned 12 weeks of treatment, for each treatment group. The results will be reported in a table and also graphically.

The primary analysis will use data from week 6 and week 12, based on actual clinic visit dates. If a subject has at least 4 recorded maximum pelvic pain scores in the 7 days prior to a clinic visit, the mean of the available scores will be calculated to be that subject’s value in the primary efficacy analysis. These values will differ slightly from the weekly reported pain score, if a subject’s clinic visit is not on the exact target date.

Comparison of AQX-1125 to placebo at Week 12 for the primary efficacy endpoint will use MMRM. SAS PROC MIXED will be used with the observed change from baseline score at Week 6 and Week 12 as dependent variables. The model will include the baseline NRS score as a fixed effect covariate with fixed effect categorical factors for treatment group, visit and baseline×visit and treatment×visit interactions. The interactions will remain in the model regardless of significance. Treatment group comparisons at each visit (including the primary analysis endpoint at the Week 12 visit) will be estimated by least squares (LS) means differences with accompanying p-values and 95% CIs.

An unstructured covariance pattern will be used to estimate the variance–covariance of the within-subject repeated measures. Sample SAS code for the primary efficacy endpoint analysis is provided in Appendix B – Sample MMRM Code.

2.2.13.2 Supplementary Analysis to the Primary Endpoint

The following supplementary analysis will be provided to support the primary efficacy analysis.

- The primary efficacy analysis will be performed on the PP Population
- The primary efficacy analysis will be performed on the ITT Population based on MI MAR data imputation (see Section 2.2.10.2)
- The primary efficacy analysis will be performed on the ITT Population based on MI MNAR data imputation (see Section 2.2.10.2)
- The primary analysis will be repeated using each observed daily value of pelvic pain score, through day 84. For this analysis, weekly average pain score will not be used, but reported daily values will be to estimate daily change from baseline values. This analysis will be an MMRM on the PP Population using Observed Cases. The model will include the baseline NRS score as a fixed effect covariate with fixed effect categorical factors for treatment group, visit and baseline×day and treatment×day interactions. Here visit is a weekly level variable. Treatment group comparisons at each day will be estimated by least squares (LS) means differences with accompanying p-values and 95% CIs. Treatment group comparisons at each day will be estimated by least squares (LS) means differences with accompanying p-values and 95% CIs. The model will adjust for the multiple subject observations using a REPEATED statement in SAS Proc Mixed

An unstructured covariance pattern will be used to estimate the variance–covariance of the within-subject repeated measures. If the model does not converge a different covariance structure (i.e., one with less parameters to estimate) will be applied.

- The weekly maximum daily pelvic pain (mean) scores and change from baseline values will be summarized by treatment group for each of the 12 weeks in the treatment period. This summary may differ slightly from the primary analysis, since the primary analysis uses the values at week 6 and week 12 from the 7 days prior to the actual clinic

visit, while this analysis will use values from the weekly visits (days 1-7, days 8-14, days 15-21, etc.).

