Subject pelvic pain as assessed by the 11-point NRS (eDiary) will be summarized at each week during the study. Analyses in the week prior to the Week 6 Visit, Week 12 Visit and Week 16 Visit (Off-Treatment Safety Follow-Up) will be produced with mean, median, standard deviation, and quartiles for both pelvic pain score and the change from baseline in pelvic pain score, using the mean of the maximum observed value from each of the 7 days prior to each visit (Baseline, Week 6, Week 12 and Week 16). This will be reported for maximum daily pelvic pain score and similarly for average daily pelvic pain score. The proportion of subjects who respond to treatment at Week 6, Week 12 and at Week 16 will be summarized. Use of concomitant analgesic medication will be summarized with the percentage (%) of subjects taking each class of medication (permitted short-acting opioid-containing analgesics and non-opioid containing analgesics: e.g., acetaminophen) and the daily dose (mean, median, standard deviation, and quartiles, using subjects who took any such medication on at least 1 of the 7 days prior to the Baseline, Week 6, Week 12 or Week 16 Visit).

Other secondary endpoints will be summarized at Baseline, Week 6, Week 12, and Week 16, including observed values at each timepoint and change from Baseline at post-baseline timepoints, with mean, median, standard deviation, and quartiles for continuous data, and counts and percentages for categorical and binary data.

Comparison of AQX-1125 to placebo at Week 12 for the primary efficacy endpoint will use repeated measures analysis of variance to compare change from Baseline in maximum pain score (NRS score) (dependent variable) between treatment arms (AQX-1125 and placebo). Baseline

maximum pain score (NRS score) will be included in the model as a covariate. Change from Baseline to Week 6 and Week 12 will be included in the analysis. A P value less than or equal to 0.05 for the change from Baseline at Week 12 will be considered statistically significant. All randomized subjects will be included in the primary analysis.

Comparison of AQX-1125 to placebo for proportion of subjects who are responders will be used to further understand the effect of AQX-1125 on pelvic pain. P values for the test of equal numbers of responders in each group will be reported, without adjustment for multiplicity, and used descriptively.

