2.2.5.3 Per-Protocol (PP) Population

The PP Population will include all ITT subjects who do not have any major protocol deviations that possibly affect interpretation of the primary efficacy endpoint and have non-missing Baseline and Week 12 assessments of maximum daily pelvic pain (i.e. the primary efficacy assessment). Determination of which subjects to be included in the PP population will be performed by a blinded review committee prior to database lock. In the event of study drug administration error, the subject will be omitted from the PP population.

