2.2.10.2 Imputation Methods

The primary endpoint analysis method is a mixed model for repeated measures (MMRM) ANCOVA. This is an observed case approach to missing data and assumes the missing data is missing at random (MAR).

Sensitivity analyses for the primary efficacy analysis will include imputing the missing data using two multiple imputation (MI) methods (described below). Any sensitivity analyses performed will be considered supportive analysis.

- Multiple Imputation Assuming Missing at Random: Missing post-baseline weekly maximum daily pelvic pain (mean) change from baseline scores at Weeks 6 and 12 will be imputed via MI assuming (MAR). SAS Proc MI using the linear regression method will be the method for the imputation if the missing data pattern follows a monotonic pattern. If the data does not follow a monotonic pattern a sequential approach to imputing the variables to produce a monotone missing data pattern as described in Alut (2012) will be applied.

A default random number generator of 345353 will be used and 100 imputed datasets will be created. Each of the imputed datasets will be analyzed via the same model as the primary efficacy endpoint analysis (See Section 2.2.13.1). The range of the imputed pain values will be set between 0 and 10 via the SAS Proc MI Maximum and Minimum options. The results across the multiple imputed data sets will be combined using SAS Proc MIANALYZE.

The following are the set of variables to be used in the MI model:

- treatment group (placebo/AQX-1125)
- age group (<65, 65-<75, ≥75 years)
- race (White/Non-White)
- baseline daily pelvic pain score
- experienced a severe AE (yes/no) (CTCAE grade 3-5, severe, life-threatening or death)
- duration of exposure [last day-first day] +1

For the ‘experienced a severe AE’ imputation variable, if a subject experiences a severe AE from baseline to Week 6 the value will be ‘yes’ for the imputation of the Week 6 time-point, ‘no’ otherwise. Similarly, if a subject experiences a severe AE from Baseline to Week 12 the value will be ‘yes’ for the imputation of the Week 12 time-point, ‘no’ otherwise.

Note: if the MI model does not converge or produce estimates (i.e., due to over-specification) the set of imputation variables may be modified.

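### The supplementary daily-diary MMRM is run on the PP Population, so the only fitted pain model that reaches back before the Week 6 window drops every man without a Week 12 value

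*SAP*

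**What the plan says.** SAP 2.2.13.2 lists the supplementary analyses. One is introduced as "The primary analysis will be repeated using each observed daily value of pelvic pain score, through day 84", followed by "This analysis will be an MMRM on the PP Population using Observed Cases". The covariance is unstructured, with a simpler, unnamed structure if the model does not converge. The same list already contains a PP run of the primary analysis.

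SAP 2.2.5.3, like protocol 10.3, admits to PP only men who "have non-missing Baseline and Week 12 assessments of maximum daily pelvic pain" and have no disqualifying deviation. SAP 2.2.13 makes ITT the primary efficacy population.

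On the primary model, SAP 2.2.13.1 states "SAS PROC MIXED will be used with the observed change from baseline score at Week 6 and Week 12 as dependent variables". On inclusion, the SAP synopsis states "All randomized subjects will be included in the primary analysis", and the protocol synopsis has the same sentence.

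**The concern.** An analysis presented as a repeat of the ITT primary analysis is restricted by something that happens after randomization: having a Week 12 value. Once men without that value are removed, an observed-case mixed model has only intermittent diary gaps left to handle. For withdrawal, it has become a completers analysis.

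This matters because daily data are what could add information about men who leave early. A man who withdraws at Week 4 with 28 diary days has no Week 6 or Week 12 row, so he adds no outcome to the primary MMRM. The daily model could use those 28 days, but the population rule discards them. If withdrawal depends on pain and differs between arms, a supportive estimate may move in either direction, and a reader may take its agreement with the primary result as more reassuring than it is.

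**Working it through.** **1. Which fitted pain analyses can use scores from before the Week 6 window?**

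| Analysis (SAP section) | Population | Pain data used |
|---|---|---|
| Primary MMRM (2.2.13.1) | ITT | Weeks 6 and 12; 7 days before each visit, at least 4 scores |
| MI under MAR (2.2.10.2) | ITT | Imputes Weeks 6 and 12; listed predictors are treatment, age group, race, baseline pain, severe AE, exposure |
| MI under MNAR (2.2.10.2) | ITT | Same variable list |
| Time-course models (2.2.13.3) | not restricted to PP | Weeks 6, 12 and 16 |
| Daily MMRM (2.2.13.2) | PP | Every diary day to day 84 |

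The weekly table for Weeks 1-12 is descriptive, and Early Termination data are summarized descriptively (SAP 2.1). The daily MMRM is therefore the only fitted pain model that includes days before the Week 6 window.

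**2. The plan's own figures.** Inputs from SAP 2.2.1: difference 1.2, SD 2.0, two-sided 5%, 10% discontinuation from study drug. The noncentral-t power is 79.5% at 44 per arm and 80.4% at 45, so 45 per arm is reproduced. Then 45 / 0.9 = 50 per arm, 100 in total. The standard error of the difference at 45 per arm is 2.0 × √(2/45) = 0.42.

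**3. How many men could be lost.** At 10%, 100 × 0.10 = 10 men, if every discontinuation also ended diary recording before Week 12. That is a ceiling for this route, because the 10% refers to study drug and the documents give no study-withdrawal rate. Assumed rates of 5% and 20% give 5 and 20.

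**4. Size and direction, under assumed inputs.**

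*Scenario A.* 200,000 simulated men per arm; 12 weekly values; random intercept and slope; true Week 12 difference 1.20; SD about 1.9; logistic dropout on the previous week's change. Losses were 5-10% on active and 8-15% on placebo. Completers gave 1.17, 1.15, 1.13 and 1.11. Regression on all observed weeks gave 1.20, 1.20, 1.19 and 1.21. The gaps are 0.03, 0.05, 0.06 and 0.10 toward the null, or 0.03/0.42 = 7% to 0.10/0.42 = 24% of one standard error.

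*Scenario B.* 400,000 men per arm; early, Week 6 and Week 12 values; SD 2; true difference 1.2; the men with the worst early change leave. Each cell shows the completers' estimate, then the estimate using everyone's early score.

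| Loss, active / placebo | Correlation 0.4 | 0.6 | 0.8 |
|---|---|---|---|
| 10% / 10% | 1.20, 1.20 | 1.21, 1.21 | 1.19, 1.19 |
| 10% / 0% | 1.35, 1.19 | 1.44, 1.21 | 1.51, 1.20 |
| 15% / 5% | 1.34, 1.21 | 1.40, 1.20 | 1.47, 1.20 |
| 20% / 0% | 1.47, 1.19 | 1.62, 1.20 | 1.76, 1.20 |

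Equal loss gives no gap. Unequal loss gives gaps away from the null from 1.34 − 1.21 = 0.13 to 1.76 − 1.20 = 0.56. Removing exactly the worst responders is an extreme mechanism.

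**5. Can the daily model be fitted as written?** An unstructured covariance over 84 days has 84 × 85 / 2 = 3,570 parameters for about 100 men, so it cannot. Over 12 weeks it has 12 × 13 / 2 = 78. Scenario A tested a 12-week analysis, not an 84-day one.

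**The case against.** The strongest reply is that nothing decisive rests on this analysis. It is one of five supplementary items, and the SAP never presents it as its missing-data analysis. That job belongs to two ITT imputation analyses, one under MAR and one placebo-based, which impute Weeks 6 and 12 for early leavers too. Protocol 10.4.2 foresees PP sensitivity runs. The early diary days still appear in the weekly table. All of this stands, and it limits the point to a supportive analysis. It does not explain why the only model using daily data is confined to PP when a PP run of the primary analysis is already listed.

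A reader might infer that everyone who stops treatment early is excluded. The documents do not support that. Men who discontinue study drug are encouraged to continue visits, with emphasis on pain data, and one who has a Week 12 value and no relevant major deviation can remain in PP.

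A reader might also infer that changing the population alone solves the problem. It does not: the 84-day unstructured model would fall back to an unnamed covariance structure, and under MAR dropout a misspecified structure need not recover the true difference.

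Finally, the all-randomized sentence can fairly be read as naming the ITT Population, with the operative sections specifying observed cases. It then needs clarifying rather than withdrawing.

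**Conclusion.** The point holds for the supplementary analysis. As written, the daily MMRM conditions on having a Week 12 value and discards all diary days of men who leave without one. No other fitted pain model or imputation model in the SAP uses scores from before the Week 6 window.

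It would be too strong to conclude that the primary result is biased by this choice, or that the supplementary estimate is biased in a known direction. The primary estimate does not depend on it. The scenarios disagree in sign and rest entirely on assumed dropout rates and mechanisms, which the documents do not supply. In the milder one the gap is at most about a quarter of a standard error. Because the direction cannot be known in advance and the remedy is cheap, the selection step is worth removing before unblinding.

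The inclusion sentence is inaccurate if read literally: a randomized man with neither a Week 6 nor a Week 12 value contributes no outcome to the primary MMRM.

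**What to change.** - **SAP 2.2.13.2:** run this supplementary analysis on the ITT Population, using all post-baseline diary data of every randomized man with a baseline, and keep the PP run as a repeat. Fit it to weekly means for Weeks 1-12 under the existing four-score rule, with unstructured covariance (78 parameters) and a named fallback structure. This would also supply the weekly least-squares means and differences promised in protocol 10.4.2.3, whose stated model holds only Weeks 6 and 12.
- **SAP synopsis, and the protocol synopsis at its next amendment:** state that all randomized subjects are in the ITT Population, but that only those with a baseline and at least one Week 6 or Week 12 value contribute to the primary MMRM. Report by arm how many do not.

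The cost is one additional model, a SAP revision before unblinding, and one protocol sentence when the protocol is next amended. No new data are needed.

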2.2.13.3 Secondary Endpoints

P values for secondary endpoints will be used for descriptive purposes rather than for statistical inference; therefore, no adjustments for multiplicity will be utilized.

The following four change from Baseline to Week 12 endpoints will be analyzed in a manner similar to the primary efficacy analysis as described in Section 2.2.13.1:

- (1) NIH-CPSI pain subscale (pain, urinary symptoms and quality of life impact) and all domains total score
 - Total score (score range 0-43)
 - Pain: Total of items 1a, 1b, 1c, 2a, 2b, 3, 4 (score range 0-21)
 - Urinary Symptoms: total of items 5 and 6 (score range 0-10)
 - QoL Impact: total of items 7,8 and 9 (score range 0-12)

NIH-CPSI data are collected on a paper form at each planned clinic visit.

- (2) Male sexual health as measured using the International Index of Erectile Function Questionnaire, Erectile Function domain (IIEF-EF): The IIEF-EF score is the sum of the ordinal responses to the 5 items

IIEF-EF data are collected on a paper form at each planned clinic visit.

- (3) Mean of average daily pelvic pain scores (eDiary), average pelvic pain (in clinic), and maximum daily pelvic pain (in clinic).

Average and maximum daily pelvic pain are collected on the eDiary, and also on a paper form at each planned clinic visit. Analysis of data collected on paper at the planned clinic visits will be used to confirm results from the analysis of data collected on the eDiary.

- (4) 24-hour voiding frequency

For each of the scheduled assessment periods, the voiding frequency will be the last 24-hour period in which voiding is collected (i.e., if voiding is collected in more than one 24-hour period).

The following four-time course secondary endpoints will be assessed by MMRM model where the change from Baseline (Visit 2) to Week 6 (Visit 3), Week 12 (Visit 4), and Week 16 (i.e. 4 weeks after end of treatment) is the dependent variable:

- (1) Mean of maximum daily pelvic pain score (eDiary)
- (2) NIH-CPSI pain subscale and all domains total score
- (3) IIEF-EF
- (4) Mean of average daily pelvic pain scores (eDiary), average and maximum pelvic pain (Paper-based NRS in clinic)

The MMRM model to assess time course will have treatment as a factor, the corresponding baseline value as a covariate, a linear term for time (in weeks), and a time×treatment interaction effect term. The model will allow for a subject random intercept and slope over time with an unstructured correlation matrix. Sample SAS code for the time course MMRM is provided in Appendix B – Sample MMRM Code.

For response to treatment as measured by the GRA and PGI-C at Week 12 (Visit 4), the frequency distribution of each response scale will be presented by treatment group and assessed using a chi-square row mean score difference test.

- The GRA response is a 7-point Likert scale (range: -3 to 3) with a score of -3 indicating “Markedly Worse”, a score of 0 indicating “No Change”, and a score of 3 indicating “Markedly Improved” to the question: *As compared to when you started the study drug, how would you rate your Chronic Prostatitis / Chronic Pelvic Pain Syndrome symptoms now?*
- The PGI-C response is a 7-point Likert scale (range: 1 to 7) with a score of 1 indicating “Very much improved”, a score of 4 indicating “No change”, and a score of 7 indicating “Very much worse” to the item: *Choose the response that best describes the overall change your pelvic pain since you started the study.*
- The PGI-S response is a 5-point ordinal scale with a score of 1 being “None” and a score of 5 being “Very Severe” to the item: *Choose the response that best described the severity of your chronic prostatitis / chronic pelvic pain symptoms over the past week.*

For response to treatment as measured by the PGI-S at Week 12 (Visit 4), the frequency distribution of each response scale will be presented by treatment group and the change from baseline will be assessed by an ANCOVA model with treatment as a factor and baseline PGI-S as a covariate.

For the following two dichotomous secondary efficacy endpoints the rates for each treatment group and difference between the treatment groups will be presented with corresponding 95% CIs. A CMH test will be used to test for differences in rates between the treatment groups controlling for baseline pelvic pain. The baseline pelvic pain will be stratified into 2 categories (4-7 and >7):

- (1) Treatment response as defined by meeting either of the following:
 - Decrease in maximum daily pelvic pain (mean) from Baseline to Week 12 using a standardized 11-point NRS with no change in the amount or strength of concomitant analgesic medications (as defined in Section 2.2.14).
 - Decrease in maximum daily pelvic pain from Baseline to Week 12 using a standardized 11-point NRS with a decrease in the amount or strength of concomitant analgesic medications (as defined in Section 2.2.14).
- (2) A $\geq 30\%$ and $\geq 50\%$ improvement (decrease) in maximum daily pelvic pain (mean) (using the 11-point NRS recorded by eDiary and the NIH-CPSI pain subscale), at Weeks 6 (Visit 3) and 12 (Visit 4).

For the Discontinuation of study medication due to treatment failure endpoint, only summary statistics will be provided for the percent meeting treatment failure criteria and the time to event (no inferential analyses will be performed). Time to discontinuation of study medication due to treatment failure will be summarized and presented graphically using Kaplan-Meier methods (i.e., SAS PROC LIFETEST stratifying on treatment group).

The frequency distribution of the 5-category IIEF-EF score will be presented by treatment group for Week 12 as well as a shift table from Baseline. The 5 categories are no erectile dysfunction (score: 26-30), mild erectile dysfunction (score: 22-25), mild to moderate erectile dysfunction (score: 17-21), moderate erectile dysfunction (score: 11-16) and severe erectile dysfunction (score: 1-10). Responses to all items must be completed to calculate an IIEF-EF score. Any response with missing values will be excluded from the analyses. Treatment group difference

with corresponding 95% CIs in the 5-category IIEF-EF will be assessed by a Cochran-Mantel-Haenszel (CMH) test using row mean scores controlling for Baseline IIEF-EF score.

Data from both treatment arms will be used to calculate a meaningful change threshold (MCT), which reports a change in the primary endpoint (change in maximum daily pelvic pain) by anchoring to other outcomes (including PGI-S and/or PGI-C) to determine a change in maximum pelvic pain that provides a meaningful benefit to patients. The determination of the MCT will be made outside of the methods documented in this SAP prior to database lock. Once the MCT is determined, the proportion of subjects who have an improvement of at least the MCT will be summarized by treatment group and compared using a chi-square test as an exploratory analysis.

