9.2.2 National Institutes of Health, Chronic Prostatitis Symptom Index

The NIH-CPSI is a commonly used 13-item questionnaire for the assessment of symptom severity in men with CP/CPPS. For each item, score ranges are 0–1 (6 items), 0–3 (2 items), 0–5 (3 items), 0–6 (1 item), and 0–10 (1 item) (Litwin et al., 1999, [Appendix 4. National Institutes of Health Chronic Prostatitis Symptom Index](#)). This will be performed at Visits 1, 2, 3, 4, ET (if needed), and at the Off-Treatment Safety Follow-up Visit.

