Appendix 4. National Institutes of Health Chronic Prostatitis Symptom Index

NIH-Chronic Prostatitis Symptom Index (NIH-CPSI)

Pain or Discomfort

1. In the last week, have you experienced any pain or discomfort in the following areas?

- | | Yes | No |
|----------------------------------------------------|---------------------------------------|---------------------------------------|
| a. Area between rectum and testicles (perineum) |  ₁ |  ₀ |
| b. Testicles |  ₁ |  ₀ |
| c. Tip of the penis (not related to urination) |  ₁ |  ₀ |
| d. Below your waist, in your pubic or bladder area |  ₁ |  ₀ |

2. In the last week, have you experienced:

- | | Yes | No |
|--------------------------------------------------------------------|---------------------------------------|---------------------------------------|
| a. Pain or burning during urination? |  ₁ |  ₀ |
| b. Pain or discomfort during or after sexual climax (ejaculation)? |  ₁ |  ₀ |

3. How often have you had pain or discomfort in any of these areas over the last week?

- ₀ Never
- ₁ Rarely
- ₂ Sometimes
- ₃ Often
- ₄ Usually
- ₅ Always

4. Which number best describes your AVERAGE pain or discomfort on the days that you had it, over the last week?

- | | | | | | | | | | | |
|--------------------------|--------------------------|--------------------------|--------------------------|--------------------------|--------------------------|--------------------------|--------------------------|--------------------------|--------------------------------|--------------------------|
|  |  |  |  |  |  |  |  |  |  |  |
| 0 | 1 | 2 | 3 | 4 | 5 | 6 | 7 | 8 | 9 | 10 |
| NO PAIN | | | | | | | | | PAIN AS BAD AS YOU CAN IMAGINE | |

Urination

5. How often have you had a sensation of not emptying your bladder completely after you finished urinating, over the last week?

- ₀ Not at all
- ₁ Less than 1 time in 5
- ₂ Less than half the time
- ₃ About half the time

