- ₄ More than half the time
- ₅ Almost always

6. How often have you had to urinate again less than two hours after you finished urinating, over the last week?

- ₀ Not at all
- ₁ Less than 1 time in 5
- ₂ Less than half the time
- ₃ About half the time
- ₄ More than half the time
- ₅ Almost always

Impact of Symptoms

7. How much have your symptoms kept you from doing the kinds of things you would usually do, over the last week?

- ₀ None
- ₁ Only a little
- ₂ Some
- ₃ A lot

8. How much did you think about your symptoms, over the last week?

- ₀ None
- ₁ Only a little
- ₂ Some
- ₃ A lot

Quality of Life

9. If you were to spend the rest of your life with your symptoms just the way they have been during the last week, how would you feel about that?

- ₀ Delighted
- ₁ Pleased
- ₂ Mostly satisfied
- ₃ Mixed (about equally satisfied and dissatisfied)
- ₄ Mostly dissatisfied
- ₅ Unhappy
- ₆ Terrible

Scoring the NIH-Chronic Prostatitis Symptom Index Domains

Pain: Total of items 1a, 1b, 1c, 1d, 2a, 2b, 3, and _____ = _____

Urinary Symptoms: Total of items 5 and 6 _____ = _____

Quality of Life Impact: Total of items 7, 8, and 9 _____ = _____

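### The SAP's item list for the NIH-CPSI pain subscale leaves out item 1d, so it reaches 20 rather than the stated 21 and, coded literally, can change 30% and 50% responder status

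*SAP*

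**What the plan says.** SAP section 2.2.13.3, in the first group of change-from-baseline endpoints, gives the scoring rule "Pain: Total of items 1a, 1b, 1c, 2a, 2b, 3, 4 (score range 0-21"). In the same block it gives "Total score (score range 0-43") for the total, "Urinary Symptoms: total of items 5 and 6 (score range 0-10") for the urinary domain, and 0-12 for quality-of-life impact (items 7, 8 and 9). It gives no item list for the total.

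Protocol Appendix 4 prints the form. Item 1d reads "d. Below your waist, in your pubic or bladder area" and is scored 1 for yes and 0 for no. The scoring key at the end of that form begins "Pain: Total of items 1a, 1b, 1c, 1d, 2a, 2b, 3, and"; the final item number is blank in the text available to us, but 1d is legible. Protocol section 9.2.2 describes the 13 items by their ranges: "score ranges are 0–1 (6 items), 0–3 (2 items), 0–5 (3 items), 0–6 (1 item), and 0–10 (1 item").

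The pain subscale is used three times in SAP 2.2.13.3: as a change from baseline to Week 12, in the time-course model to Week 16, and in the dichotomous endpoints of at least 30% and at least 50% improvement at Weeks 6 and 12, which are assessed "using the 11-point NRS recorded by eDiary and the NIH-CPSI pain subscale".

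**The concern.** The item list and the range on one line of the SAP cannot both be right. Every other description of the instrument sides with the range, and neither document says that 1d was dropped on purpose.

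A programmer who codes the list as written gets a subscale without the pubic/bladder location item. Nothing downstream need reveal this. A seven-item sum runs from 0 to 20, and all of those values lie inside 0-21, so a check for out-of-range values passes. The continuous endpoints could move by at most 1 point per subject. The percentage-improvement endpoints are more exposed, because one point in the numerator or denominator can carry a subject across the 30% or 50% line.

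**Working it through.** **Inputs.** Item maxima come from the Appendix 4 form and agree with protocol 9.2.2: items 1a, 1b, 1c, 1d, 2a and 2b are 1 each; item 3 is 5; item 4 is 10; items 5 and 6 are 5 each; items 7 and 8 are 3 each; item 9 is 6.

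**Stated ranges.**
- SAP list (1a, 1b, 1c, 2a, 2b, 3, 4): 1+1+1+1+1+5+10 = 20. The stated 21 is not reproduced.
- With 1d added: 20+1 = 21. The stated figure is reproduced.
- All 13 items by the ranges in protocol 9.2.2: 6×1 + 2×3 + 3×5 + 1×6 + 1×10 = 43, the stated total.
- Sum of the SAP's three domains as listed: 20+10+12 = 42. With 1d: 21+10+12 = 43.
- Protocol 9.2.2 counts six items scored 0-1. The SAP list contains five.

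**Change scores.** The error in the change equals the change in 1d. It is zero when 1d is the same at both visits and 1 point otherwise.

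**Responder status.** Let B and F be the correctly scored baseline and follow-up, and d0 and d1 the 1d answers (1 or 0) at those visits. Correct improvement is (B − F)/B. Improvement as written is ((B − d0) − (F − d1))/(B − d0). All pairs were enumerated with exact integer comparisons for B from 8 to 21. That range is an assumption, since the documents give no distribution for the subscale. There are 21 reachable follow-up scores per baseline.

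| 1d at baseline, follow-up | Threshold | Pairs that change status | Direction as written | Example |
|---|---|---|---|---|
| yes, yes | 30% | 4 of 294 | becomes responder | 14 to 10: 28.6% correct, 4/13 = 30.8% as written |
| yes, yes | 50% | 7 of 294 | becomes responder | 15 to 8: 46.7% correct, 7/14 = 50.0% as written |
| yes, no | 30% | 10 of 294 | becomes non-responder | 15 to 10: 33.3% correct, 4/14 = 28.6% as written |
| yes, no | 50% | 7 of 294 | becomes non-responder | 14 to 7: 50.0% correct, 6/13 = 46.2% as written |
| no, yes | 30% | 13 of 273 | becomes responder | 10 to 8: 20.0% correct, 3/10 = 30.0% as written |
| no, yes | 50% | 13 of 273 | becomes responder | 10 to 6: 40.0% correct, 4/10 = 50.0% as written |
| no, no | either | 0 of 273 | unchanged | none |

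The denominators are 14 baselines × 21 = 294 when 1d is yes at baseline. When 1d is no at baseline, B cannot exceed 20, giving 13 × 21 = 273. Each affected baseline changes status at exactly one follow-up score. With yes at both visits and the 30% threshold, the four pairs are 11 to 8, 14 to 10, 17 to 12 and 21 to 15.

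**Without the assumed baseline range.** Over every seven-item baseline from 1 to 20, every follow-up from 0 to 20 and all four 1d patterns (20 × 21 × 4 = 1,680 combinations), 40 change status at 30% (14 lost, 26 gained) and 40 at 50% (10 lost, 30 gained). That is 40/1,680 = 2.4% at each threshold. These are counts of possible score pairs, not expected frequencies in the trial.

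**The case against.** The strongest reply is that the slip corrects itself. The printed 0-21 and 0-43 hold only with 1d, and the form, its key and the item count in protocol 9.2.2 all agree. A programmer who uses the form's own key, or who compares the theoretical maximum with the printed range, will score correctly. The SAP is therefore inconsistent with itself rather than clearly specifying a 20-point scale. This stands as an account of intent and is a good reason to rate the point low. It does not remove the need for a correction, because protocol section 10 leaves full analysis details to the SAP, and a check for out-of-range values would not catch the omission.

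It can also be said that counts of affected baselines look larger than they are. Ten of 14 baselines for the yes-then-no pattern at 30% is only 10 of 294 score pairs, or 3.4%. That is fair, and the pair counts above are the better description. The 8-21 range has no support in the entry criteria either: they require a total of at least 15, to which the urinary and quality-of-life domains can contribute up to 22, so no floor for pain follows. The 1,680-combination grid avoids that assumption and leads to the same conclusion.

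The 42-point total is conditional. It arises only if the total is built from the SAP's listed domains; summed from the 13 form items, the total is correct. It should not be counted as a second error.

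Finally, items 3 and 4 carry 15 of the 21 points and still register the frequency and intensity of pain at the 1d site.

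**Conclusion.** The concern holds. The SAP list omits 1d, reaches 20 instead of 21, and contradicts both its own stated range and the protocol's scoring key. If the list is programmed literally, the subscale is wrong by 1 point at each visit where 1d is answered yes. The change score is then wrong by 1 point when that answer differs between visits, and 30% or 50% responder status can be wrong in either direction. That consequence depends on literal programming. How many subjects would be affected cannot be determined from the documents.

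The primary endpoint and the sample size do not depend on this scale, P values for secondary endpoints are descriptive, and the same rule would apply to both arms; no bias between arms is claimed. It is a definite but low-severity scoring error that should be fixed.

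**What to change.** Before database lock and unblinding, amend SAP section 2.2.13.3 so that the pain domain is the sum of items 1a, 1b, 1c, 1d, 2a, 2b, 3 and 4 (0-21), and add a sentence stating that the total is the sum of the three domains (0-43). Check that the derivation program uses the same eight items. A test record with every item at its maximum should return 21 for pain and 43 for the total.

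The cost is one item label, one sentence and a program check. Item 1d is already on the form, so no new data are needed and power is unaffected. Made after unblinding, the same correction would be a post hoc change to an efficacy derivation.
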